### 2.1.3. Prior Clinical Studies

The first case of esophageal trauma associated with left atrial posterior wall ablation for atrial fibrillation was reported in 2003 (Lequerica JL B. E., 2008). Since then there have been a myriad of interventions in hopes of preventing such damage. This ranges from mechanical manipulation of the esophagus to esophageal cooling with various mechanisms including ice water lavage. This also includes the development of a cooled intraesophageal balloon with mixed results (Berjano EJ, 2005) (Lequerica JL B. E., 2008) (Lequerica JL B. E., 2008) (Tsuchiya T, 2007) ]. Further in-vitro evaluation of animals has been performed using a controlled saline circulating system (EPSac) which spares the esophagus from collateral thermal injury (Arruda MS, 2009). The novel idea of cooling the esophagus to prevent transmural damage has been documented as overwhelmingly positive. The most notable clinical evaluation of an esophageal cooling mechanism was performed by Tsuchiya et. which included a cooled water-irrigated intraesophageal balloon. (Tsuchiya T, 2007) A limitation of this study included the inability to assess the deeper muscular layer of the esophagus for evidence of injury. Several limitations to the above mentioned approaches include cost, physician availability, displacement of the esophagus, and ability to monitor the luminal esophageal temperature (LET).

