Data from animal models show that the muscular layer is disrupted and necrotic myocytes are seen at the border of lesions in the esophagus even when no lesions on the epithelial layer were found, suggesting that cooling the deep muscular layer of the esophagus may be needed to prevent esophageal injury.[11] Prevention of esophageal injury via cooling of the esophagus has been investigated with mathematical modeling, preclinical models, and in the clinical arena. A finite element model in three dimensions investigating the effects of a cooled intra-esophageal balloon suggested that this approach could be a viable method to prevent thermal injury to the esophagus during intraoperative ablation of the left atrium.[12] Specifically, the authors found that (i) chilling the esophagus by means of a cooled balloon placed in the lumen minimizes the lesion in the esophageal wall compared to the cases in which no balloon is used (a collapsed esophagus) and with a non-cooled balloon; (ii) the temperature of the cooling fluid has a more significant effect on the minimization of the lesion than the rate of cooling (the thermal transfer coefficient for forced convection); and (iii) pre-cooling periods previous to RF ablation do not represent a significant improvement. Finally, the authors also suggest that the use of a cooled balloon could affect the transmural region of the atrial lesion, especially in the cases where the atrium is of considerable thickness (or in other words, in the presence of an atrium of considerable thickness, when a short duration and a low target temperature are programmed, the use of a cooled balloon could reduce the possibilities of achieving a transmural lesion in the atrium.

Subsequent study using an agar phantom-based model that was built to provide temperature readings at points between the esophageal lumen and the myocardium found that this method was able to provide effective thermal protection, although it was noted that the method could fail under certain unfavorable topical and procedural conditions.[13] In this study, a balloon utilizing water temperature of 5° C flowing at a rate of 25 mL per minute was used, which likely significantly limits the capability of this device to extract heat effectively.

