Further study by this same group utilized varying coolant temperatures between 5°C and 37°C but maintained the coolant flow rate at 25 mL per minute.[14] The authors conclude that their results suggest that it is possible to thermally protect the esophagus (including the transmural region 2 mm away from the mucosal surface) during radiofrequency cardiac ablation by means of a cooling balloon placed in the esophageal lumen utilizing coolant temperature of 5°C or less and involving a precooling period of two minutes.

A custom developed system utilizing temperature controlled saline or water circulating at a flow rate between 50 to 300 mL per minute and a temperature of 5 to 25°C was evaluated using an in vitro Lamb heart – esophagus preparation, followed by an in vivo model with six dogs.[15] This custom system consisted of a 12 French probe with a distal expandable compliant latex sack with a diameter of up to 3 cm fully expanded. The authors found that a circulating water temperature of 25° C failed to spare the esophagus from thermal injury. However lowering the circulating temperature to 10° C or 5°C spared thermal injury (although expanding the balloon diameter by increasing circulating volume substantially to

intentionally displace the esophagus towards the left atrium allowed the development of shallow esophageal injury to the external layers of the muscularis).

A clinical study [16] of eight patients used a closed loop system with low flow rates (25 mL/min) and a water temperature of  $4.5 \pm 3.1^\circ\text{C}$  to build upon computer modelling demonstrating that a cooled balloon catheter (with a diameter of 10 mm) could transmurally cool the esophagus. They found that without cooling, esophageal temperature increased from a baseline of  $36.4^\circ\text{C}$  up to  $40.5^\circ\text{C}$  in under 30 seconds during ablation, whereas with the esophageal cooling balloon, esophageal temperature decreased down to  $30.2^\circ\text{C}$  with the balloon in place, and allowed an increase in temperature to only  $33.5^\circ\text{C}$ . The authors conclude that luminal esophageal temperature during the left atrial ablation was lowered by esophageal cooling using their catheter to a level where no thermal damage to the esophagus would likely be induced.

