**4.2.2. Secondary Endpoints**

- 1) Safety of the EnsoETM placement as measured by the number of adverse events recorded
- We believe that cooling of the esophagus will lead to a reduction of esophageal damage. The use of an EnsoETM would replace LET monitoring during ablation of the posterior aspect of the left atrium. This endpoint was chosen to prove that replacing the LET monitor with a cooling catheter is a safe alternative.
- This is of primary importance as any evidence of esophageal damage or adverse events related to the use of the EnsoETM would deter any further use of this approach to Pulmonary Vein Isolation (PVI).
- 2) Altered submucosal tissue architecture as assessed by endoscopic ultrasound (EUS)
- While mucosal injury may suggest significant thermal injury to related to RF ablation there is also concern that this injury may be more of a mechanical process from TEE and LET monitoring. We aim to assess the submucosa using EUS for differentiation between superficial and deep injury which may provide further insight into the risk of atrio-esophageal fistula formation. A grading scheme has not been developed for this type of evaluation so we will assess for individual changes with pre-procedure to post-procedure comparison.

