## 7. Study Procedures and Schedule

### 7.1. Study Procedures/Evaluations

#### 7.1.1. Study Specific Procedures

- Study specific imaging will include endoscopic evaluation of the esophagus one day before surgery at the time of the pre-op Transesophageal Echocardiography (TEE) and again 1-day post-op. This will include endoscopic esophageal intubation with visual assessment of the entire esophagus and grading of lesions. Coupled with this procedure will include endoscopic ultrasound assessment of the esophagus at the level of the left atrium with specific attention to the sub-mucosal layer that separates esophagus from the cardiac tissue. The patient will undergo moderate sedation during this procedure, which will accompany the TEE.
- The ECD will be placed by trained study staff following endotracheal intubation. Proper positioning will be verified. A temperature probe will be placed to verify the patient's core temperature. The target temperature will be set to the core temperature at the beginning of the procedure. Two minutes prior to ablation on the posterior wall the target temperature will be changed to the minimum temperature setting which will allow for maximal cooling. Cooling will take place throughout the duration of posterior wall ablation. After ablation in this territory is complete the target temperature will return to the patient's core temperature. The device will be removed at the completion of the procedure by anesthesiology when there is no further need for an orogastric tube.
- LET monitoring will not be performed in the patients of the intervention group as the ECD is prohibitive. Therefore, ice lavage of the esophagus, as detailed below, will not be performed in this group.

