## **7.2. Radiographic Procedures/Evaluations**

### **7.2.1. Esophagoscopy**

The patient will present for endoscopic evaluation the day prior to surgery. During this time the patient will undergo moderate sedation with continual monitoring of vital signs. Following adequate sedation the proceduralist will proceed with esophageal intubation with visual assessment of the entire esophagus and grading of lesions (Zargar classification). Furthermore, the submucosal tissue will be assessed with EUS at the level of the left atrium. This procedure will be preceded by TEE with moderate sedation maintained.

The day following the PVI the patient will undergo repeat endoscopic evaluation of the esophagus in the same manner as detailed above. The proceduralist will document their findings including the condition of the sub-mucosal esophageal tissue as noted by EUS.

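### The EUS endpoint and procedure name only the submucosa, wrongly described as the layer between esophagus and heart, so muscle-confined injury falls outside the endpoint

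*Protocol*

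**What the plan says.** The EUS endpoint is the second secondary endpoint in Protocol section 4.2.2: "Altered submucosal tissue architecture as assessed by endoscopic ultrasound (EUS"). Its stated purpose is this: "We aim to assess the submucosa using EUS for differentiation between superficial and deep injury". The section adds that the result may shed light on the risk of atrio-esophageal fistula. On scoring it says: "A grading scheme has not been developed for this type of evaluation so we will assess for individual changes", comparing the examination before the procedure with the one after.

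The procedure text follows the same line.
- Section 7.1.1 directs the EUS examination at left atrial level "with specific attention to the sub-mucosal layer that separates esophagus from the cardiac tissue".
- Section 7.2.1 says that "the submucosal tissue will be assessed with EUS at the level of the left atrium". For the day after ablation, the condition of the submucosa is the only EUS finding it names for documentation.
- Section 7.3.2 (Visit 2) names the submucosal tissue only.
- Section 7.3.3 (day-after examination) gives the anatomical region and names no layer.

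The background sections look elsewhere in the wall. Section 2.2 cites animal data with a disrupted muscular layer and necrotic myocytes where the epithelium showed no lesion, and infers that "cooling the deep muscular layer of the esophagus may be needed to prevent esophageal injury". Section 2.1.3 lists as a limitation of the most notable clinical cooling study its "inability to assess the deeper muscular layer of the esophagus for evidence of injury".

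**The concern.** There are two faults, and they compound each other.

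First, the instruction in 7.1.1 names one structure and describes another. The submucosa is an inner layer of the esophageal wall with the muscle outside it. What lies between that layer and the atrium is the muscle and then the tissue around the esophagus. A reader who follows the name and a reader who follows the description would look at different tissue. No grading scheme exists to settle which is meant.

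Second, the layer that the rationale treats as the site of hidden injury appears in no endpoint or procedure section. The primary endpoint grades the mucosa and the EUS endpoint is defined on the submucosa. An injury confined to the muscle or to the tissue beyond it meets neither definition.

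What is at stake is the validity of the one measurement meant to tell deep injury from superficial injury and to inform thinking about fistula. This cannot be left to a later analysis plan: layer findings that nobody recorded at the examination cannot be recovered in the analysis.

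**Working it through.** The plan gives no figure for this endpoint (no event rate, effect size or power), so there is nothing to reproduce. The check is a comparison of sections.

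**Step 1. Which layers do the endpoint and procedure sections name?**

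| Protocol section | Examination | Layer named |
|---|---|---|
| 4.2.1 and Table 1 | Endoscopic grading (primary) | Mucosa |
| 4.2.2 | EUS endpoint | Submucosa |
| 7.1.1 | EUS procedure, both days | Submucosa (specific attention) |
| 7.2.1 | EUS, day before and day after | Submucosa |
| 7.3.2 | EUS, Visit 2 | Submucosa |
| 7.3.3 | EUS, day after ablation | None; region only |

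The muscular layer and the tissue between wall and atrium appear in none of these rows.

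**Step 2. Where does the background locate the injury of concern?**

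| Protocol section | Evidence cited | Location |
|---|---|---|
| 2.2 | Animal models | Muscular layer, with epithelium free of lesions |
| 2.2 | In vitro and dog study of a cooled balloon | External muscularis, only when the balloon was enlarged to displace the esophagus |
| 2.1.3 | Earlier clinical cooling study | Deeper muscular layer not assessed; called a limitation |

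**Step 3. Is the anatomical description right?** The protocol's own terms, a deep muscular layer and external layers of the muscularis, put muscle on the outer side of the wall. That agrees with ordinary anatomy: mucosa, then submucosa, then muscle. The submucosa therefore cannot be what separates the esophagus from the cardiac tissue.

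**Step 4. Follow one pattern through the endpoints.** Take the pattern that 2.2 reports: muscle damaged, epithelium intact. Suppose the submucosa also looks unchanged. The mucosal grade does not change, and the EUS endpoint as defined in 4.2.2 does not change either. Whether the muscle finding is written down depends on the individual reader, because no section asks for it. An injury that also alters the submucosa would still be captured, so the gap concerns only injury that spares that layer.

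**Step 5. Does the gap fall on one arm?** The wording is the same for both arms. Section 2.2 does not say that the muscle necrosis arose under cooling, so controls can show it too. Section 7.1.2 allows iced saline lavage in participants with temperature monitoring, so luminal cooling is not confined to the device arm. The sections do not show which arm would lose more findings.

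**The case against.** The strongest reply is that the text sets an emphasis and excludes nothing. Section 7.1.1 orders EUS of the esophagus at that level and asks for particular attention to one layer. Section 7.2.1 has the proceduralist document findings that include the submucosa, which is open-ended, and 7.3.3 names no layer. The protocol also seems to use *sub-mucosal* loosely for whatever lies beneath the mucosa: the notes after Table 1 in 4.2.1 speak of sub-mucosal damage as a forerunner of fistula. The phrase about the cardiac tissue may simply point the reader to the atrial side. And because EUS is added here, the study does not have the same inability that 2.1.3 criticises.

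Much of this stands. Nothing prohibits recording a muscular change, and the means to look deeper are present. A claim that the plan prescribes a submucosa-only reading would go too far. A claim that it simply repeats the earlier study's limitation would also go too far. Disagreement between several readers is a weak worry as well, since this is a single-center study and 9.2.1 speaks of one blinded evaluator.

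The reply does not remove the point. If *sub-mucosal* was meant loosely, no section says so, and the endpoint definition in 4.2.2 still turns on submucosal architecture. A finding that may be recorded but is not part of the endpoint does not serve the endpoint's aim.

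A reader might also infer a bias in favor of the device: cooling acts from the lumen, so residual injury would sit in the outer wall where the endpoint does not look. The documents do not support that as a finding. No section compares protection by layer. The one report of residual outer-muscle injury ("allowed the development of shallow esophageal injury to the external layers of the muscularis") concerns a balloon enlarged to push the esophagus towards the atrium; without that, circulating water at 10 °C or 5 °C spared thermal injury. The study device is a tube of at most 13.3 mm outside diameter (6.6), and no intentional displacement is described.

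**Conclusion.** The point holds as a defect of endpoint definition. The layer description in 7.1.1 is wrong. The endpoint in 4.2.2, with the procedure text in 7.1.1, 7.2.1 and 7.3.2, names only the submucosa, while sections 2.1.3 and 2.2 direct concern to the muscular layer. Injury confined to the muscle or the tissue beyond it lies outside the endpoint and could go unrecorded in either arm.

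The size cannot be quantified from the documents, which do not say how often such injury spares the submucosa. With 6 subjects randomized 1:1, and assuming arms of 3 and 3, a reader might compute that one missed injury shifts an arm's rate by 1/3, about 33 percentage points. That is the arithmetic of any single misclassification in an arm of three. It is not an estimate of bias, and 4.2.2 defines no EUS event rate, only individual changes. Nor is every reading affected; only injury sparing the submucosa is.

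The consequence is for measurement validity and interpretation of an ungraded secondary endpoint in a pilot, with no bearing on error rates or sample size. The change is worth making before enrollment. Two assumptions underlie this: that EUS can distinguish the wall layers, as the protocol presumes when it singles one out, and that the case report form, which is not shown, does not already ask for findings by layer.

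**What to change.** Use one definition, in identical words, in sections 4.2.2, 7.1.1, 7.2.1, 7.3.2 and 7.3.3: *new change from the pre-ablation EUS in any esophageal wall layer (mucosa, submucosa, muscularis propria) or in the tissue between the wall and the left atrium, recorded by layer at both examinations*.

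In 7.1.1, delete the clause that describes the submucosa as separating the esophagus from the cardiac tissue.

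The cost is a protocol wording change and a few added lines on the EUS form. The examinations and the reader stay the same, and no procedure is added. The small downside is a few more descriptive items to record and report.

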#### 7.1.2. Standard Care Procedures

- Medical History will be obtained by interview and will involve identification of contraindications to the use of the ECD. This includes a history of esophageal perforation or varices. An allergy to silicone will be assessed.
- The patient's active medication list will be reviewed as is standard protocol for atrial fibrillation ablation, but this is not specific to the study as there are no medications that would impact the use of the ECD.
- All subjects will be on Protonix (40mg; twice daily) immediately following surgery for 30 days and anticoagulation for 3 months following surgery.
- The physical exam will be performed as is customary for the procedure. Study specific exam is included as part of the airway assessment which is performed on a regular basis by anesthesiology. The oropharynx will be assessed prior to placement of the ECD.
- The patient will be administered general anesthesia by the anesthesia department with hemodynamic monitoring. Two 8-French sheaths placed in the right femoral vein. A 7- and a long 9-French sheath will then be placed in the left femoral vein and a 7-French sheath placed in the right subclavian vein. Under fluoroscopic guidance, a quadripolar catheter is then placed through the left femoral venous sheath to the His bundle region. His-bundle electrocardiography is performed with measurement of intervals. A decapolar catheter with 2-5-2 spacing is then placed through the right subclavian venous sheath and utilized to intubate the coronary sinus for left atrial recordings. Ventricular pacing is used to demonstrate VA 1:1 conduction. Next, trans-septal puncture is performed with the use of a SL-1 sheath from Daig, a Baylis needle, and intracardiac echocardiography. Then, a separate slightly higher puncture of the atrial septum is performed with intracardiac echo guidance into the left atrium also using a Baylis needle and SL-1 sheath. The participant will be given 5000 units of heparin bolus after the first transseptal puncture and again after the second transseptal puncture. The participant will then be maintained on heparin infusion with intermittent boluses to maintain ACT between 300 and 350 seconds. At this point, a multi-pole loop catheter will be placed through the sheath into the left atrium. Three-dimensional geometry will be obtained of all four pulmonary veins, left atrial appendage, and left atrium. Then, the loop catheter will be placed in the left superior vein and ablation will be carried out utilizing an 8 mm distal tip large curve ablation catheter from Boston Scientific. Ablation will be carried out with 35 watts of energy at 55 degree temperature on the posterior wall and 50 watts of energy and 55 degree temperature on the anterior wall. The participants with LET monitoring may require intermittent boluses of iced lavaged saline through the nasogastric tube when the temperature rises above 1 degree centigrade. Next, ablation will be carried out of the left superior pulmonary vein until completely isolated as well as the carina. The loop catheter will then be placed in the left inferior pulmonary vein and isolation of the left inferior pulmonary vein is obtained as well. The loop catheter will then be placed in the right superior pulmonary vein with isolation of that catheter and then brought down into the right inferior pulmonary vein with entrance block demonstrated from that catheter. All veins then demonstrate exit block with additional consolidating ablations as required. All four veins will be checked at that point. Next, Isuprel provocation will be initiated. Pacing will be

performed to the atrioventricular (AV) nodal Wenckebach block rate and to the AV nodal effective refractory period. Then the patient is placed on 10-20 mcg of Isuprel and repeat burst pacing from the coronary sinus as well as the high right atrium is performed. Should atrial fibrillation recur then further ablation is carried out from the roof anteriorly from the right superior pulmonary vein to the left superior pulmonary vein with bidirectional conduction block detected. A complex atrial fractionated electrogram map may be performed to determine fractionated areas for further ablation lines. Should atrial fibrillation persist then anterior septal ablation will be carried out for complex atrial fractionated electrograms as well as spot ablation within the atrial appendage or atrial appendage isolation if required. Should the patient develop mitral isthmus atrial flutter then an ablation line will be performed from the left inferior pulmonary vein to the mitral annulus posteriorly. Should the patient develop typical atrial flutter, a cavo-tricuspid isthmus (CTI) right atrial flutter line may be performed. Other right atrial lesions will be targeted as required, including superior vena cava isolation if needed. Organized atrial tachycardias will be mapped and ablated as needed. At the conclusion of the ablation, heparin is discontinued and catheters removed. Sheaths are removed once the (activated clotting time) ACT is below 180 seconds or following administration of protamine. At the conclusion of the procedure the intracardiac echocardiogram is used to demonstrate no evidence for pericardial effusion or fluid.

